As a further analysis, a logistic regression model on each binary endpoint at Week 16 with fixed factors for 'treatment', and 'region' as strata will also be applied for the FAS. The estimates from the logistic regression are on the logit scale, and the difference in proportions will be calculated as the difference between the predicted probabilities in the treatment groups on the original scale, with the confidence interval calculated using the cumulative distribution function method of Reeve [[R16-4414](#)]; further details will be provided in the TSAP.

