7.5 DETERMINATION OF SAMPLE SIZE

Calculations were performed using R Version 3.5.1.

The study is intended to show a benefit of BI 655130 over placebo in terms of the difference in % PPP ASI change at Week 16.

The aims of this study are two-fold. A first aim is to show a significant non-flat dose-response curve across the different doses and placebo. Additionally to that at least one modelled dose within the dose range considered should show a benefit of at least "Delta" % PPP ASI change compared to placebo. The probability of success of this trial is therefore defined as the probability to (1) obtain a significant test for non-flat dose-response curve and (2) to observe for at least one of the modelled doses an effect difference of at least delta compared to placebo.

The sample size calculation is based on an assumed maximum difference in % PPP ASI change of placebo vs. BI 655130 of 30%, as well as on the pre-specified models listed in [Section 7.2.2](#). The standardized deviation of the % PPP ASI change is assumed to be 35%.

For placebo, a fixed rate of -25% PPP ASI change at Week 16 will be considered. These estimates are derived from trial 1368.15 in PPP.

Using a total sample size of 140 evaluable patients (40, 20, 20, 20 and 40 for placebo and low to high dose regimes respectively), the probability for a successful trial (as defined above) was estimated using simulations. For each dose group, samples of the required size were drawn from a normal distribution. Values smaller than -100% (which corresponds to complete recovery of a patient) were set to -100%. The expected values of the original normal distribution were chosen such that the expected dose group means after truncation correspond to the model assumptions. In the following, the reported dose means will always refer to dose means after truncation. The standard deviation of the untruncated normal distribution was set to 35% for all simulations. This will result in slightly reduced standard deviations after truncation (of approx. 30% for the highest dose group).

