6.3 PATIENT SETS ANALYSED

The following analysis sets will be defined for this trial:

Enrolled set (ES)

This patient set includes all patients who signed informed consent. It will be used for display of patient disposition.

Randomized set (RS)

This patient set includes all patients who were randomized in the trial. Treatment assignment will be as randomised. It will be used for display of disposition, IPD and etc.

Safety analysis set (SAF)

This patient set includes all patients who were randomised and received at least one dose of study drug. It will be the main analysis set for presentation of safety data. Patients will be analyzed according to the actual treatment.

Safety analysis set – Post Week 16 (SAF-post 16)

This patient set includes all patients in SAF who received at least one dose of study drug after, and including, Week 16. It will be the main analysis set for presentation of safety data after Week 16 only. Patients will be analyzed according to the actual treatment after week 16.

Full Analysis Set (FAS)

This patient set includes all patients who were randomised, received at least one dose of study drug and had a baseline for the primary endpoint. Treatment assignment will be as randomised. This is the main analysis set for presentation of efficacy data.

Full Analysis Set – Post Week 16 (FAS-post 16)

[figure not shown]
This patient set includes all patients in the FAS and had received at least one dose of study drug after, and including Week 16. Treatment assignment will be as randomised. This is the set for additional analysis of efficacy data post Week 16.

Per-Protocol Set (PPS)

This patient set includes all patients in the FAS set who adhered to the CTP without any iPDs which are flagged for exclusion from the PPS in the table above. The PPS will be used for sensitivity analysis on the primary efficacy endpoint.

Modified FAS set (m-FAS)

This patient set includes all patients in the FAS set excluding pre-identified questionable cases (mild cases) based on mQC (medical quality control) review where the severity of PPP could not be clarified and confirmed based on the descriptive review and quality control of the photo documentation. The m-FAS will be used for sensitivity analysis on the primary efficacy endpoint and selected secondary endpoints.

Handling of Treatment Misallocations in Analysis Sets

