7.4 PRIMARY ENDPOINT

For the primary endpoint analysis, first a mixed effect model for repeated measurements (MMRM) is calculated to estimate the treatment effects and the corresponding covariance matrix. Using the MCPMod approach ([11](#), [12](#)), these estimates are then further used to (1) test for a non-flat dose response curve and (2) to identify suitable dose-response shapes out of a selection of candidate models. The final model will then be calculated by averaging over all significant model shapes.

Details on both the specification of the MMRM and the MCPMod approach are given in the CTP Section 7.2.2. Sample size calculations are described in CTP Section 7.5.

The primary analysis of primary endpoint will be based on the FAS. Any data collected after use of any rescue therapy or after 6 weeks following last drug administration if a patient

discontinued treatment early will be censored as the primary estimand (EC).

MMRM analysis

The % change in PPP ASI from baseline (Visit 2), at Visits 3, 4, 5, 6, 7, 8 and 9 (Weeks 1, 2, 3, 4, 8, 12 and 16) will be evaluated using an MMRM accounting for the following sources of variation: 'baseline' as a continuous covariate, and 'visit', 'treatment', 'region' (stratification according to Japan vs. non-Japan), 'visit*treatment' and 'visit*baseline' interaction as fixed effects as well as the random 'subject' effect. The unstructured covariance structure will be used to model the within patient measurements. To estimate denominator degrees of freedom the Kenward-Roger approximation will be used.

In the event of model non-convergence, the methods described in [Section 9.3](#) will be utilized to resolve this.

SAS code for MMRM:

The following SAS code will be used to calculate the MMRM.

```
PROC MIXED DATA=alldat cl method=reml;
  CLASS visit trt stratum subject;
  MODEL ept = stratum visit*trt base*visit / ddfm=kr s CL;
  REPEATED visit / subject= subject type=un r rcorr;
  LSMEANS visit*trt / pdiff=all om cl alpha=0.05 slice=visit;
RUN;
```

Results of the MMRM (N, mean, SE and 95% CI per dose group and timepoint) will be presented in tables and displayed graphically.

MCPMod Analysis

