7.5.2 Secondary endpoints

Continuous secondary endpoints

Continuous secondary endpoints up to week 16 will be evaluated using MMRM model and MCP-Mod in the same way as for the primary endpoint.

For percent change in PPP ASI from baseline at Week 52, a similar setting to that described for the primary endpoint MMRM model (in [Section 7.4](#)) will be applied with the inclusion of the additional visits of Week 28, 40 and 52.

Binary secondary endpoints

For each of the binary secondary endpoints at Week 16, a logistic regression and MCPMod model will be used to evaluate the treatment effect of multiple doses of Spesolimab vs. placebo. This method will be implemented for MCPMod in a binary setting.

The primary analysis of binary secondary endpoints will be based on the FAS. Any data collected after use of any rescue therapy or after 6 weeks following last drug administration if a patient discontinued treatment early will be censored as the primary estimand (EC).

Logistic regression analysis

For binary endpoints, the difference in the proportion of patients with a response between Spesolimab and placebo will be analysed, for the FAS, using a logistic regression approach with a logit link via PROC LOGISTIC in SAS[®]. Fixed classification effects will include treatment and region (Japan vs. Non-Japan). In case 0 event is observed in any of the combination of dose group and strata a penalized regression based on the Firth's bias reduction method ([19](#), [20](#)) will be used.

The estimates from the logistic regression are on the logit scale, and the difference in proportions will be calculated as the difference between the predicted probabilities in the treatment groups on the original scale. Odds ratio will be also reported between each Spesolimab arm vs placebo

Confidence intervals will be calculated using the cumulative distribution function method of Reeve (14). More specifically, as suggested in Reeve (14), a numerical search algorithm will be employed to find the quantiles x_A of the cumulative distribution function, $F_{\widehat{\Delta p}}$, such that $F_{\widehat{\Delta p}}(x_A) = A$, where $A = 2.5\%$ and $A = 97.5\%$ and $F_{\widehat{\Delta p}}$ is given by equation (10) in Reeve (14). R code that will be used to implement this is provided in [Section 9.2](#).

MCP-MOD analysis

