The estimate of response rate from each dose group obtained via logistic regression or penalized regression based on the Firth's bias reduction method (as described above) without intercept will be used as basis for the MCPMod analysis of the binary secondary endpoints. The subsequent MCP-Mod analyses are based on the response rates on the logit scale.

The multiple comparison procedure will be implemented using optimal contrast tests which control the family-wise type I error rate at a one-sided $\alpha = 0.05$. The same candidate models as for the primary endpoint will be used for all secondary binary endpoints. For the MCPMod test, the optimal contrasts of each candidate model are calculated using the R-function `optCont` using weights (w) proportional to the sample size of each dose group, respectively, and are shown in [Table 7.5.2: 1](#). These contrasts will be recalculated using the actual sample size of the dose groups (in case this differs from the planned numbers). The final contrasts will be presented in the CTR.

Table 7.5.2: 1 Contrast coefficient

Model	Contrast coefficients for (total) dose				
	Placebo	Low dose: [REDACTED]	Medium-low dose: [REDACTED]	Medium-high dose: [REDACTED]	High dose: [REDACTED]
Linear	-0.783	-0.049	0.049	0.196	0.587
E _{max}	-0.869	0.112	0.151	0.190	0.416
Exponential	-0.574	-0.194	-0.118	0.106	0.780
Logistic	-0.706	-0.220	0.036	0.279	0.612
Sigmoid E _{max}	-0.638	-0.247	-0.052	0.256	0.681

BI: Spesolimab total dose, [REDACTED] administered before week 16.

The MCP-Mod test will be applied using these fixed contrasts. R code is also available in [Section 9.4.2](#).

[figure not shown]
All significant dose-response models will be re-fitted to the data without any parameter assumptions to generate a set of new estimates of the model parameters from the data. The final model is derived as a weighted average over all significant model shapes obtained via the same averaging procedure as described for the primary endpoint.

The following displays are planned.

- Table of the contrast coefficients per dose group and candidate model, together with the MCPMod test statistics and p-values for each model and the critical value
- For the average model, figure of the dose-response curve
- For all significant model shapes, figures of the dose-response curve plus 95% confidence band (of the predicted shape)

Descriptive statistics

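### The binary Week 16 models omit the baseline severity that the other Week 16 models adjust for; adding it may recover modest power on secondary endpoints

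*SAP*

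**What the plan says.** The binary secondary endpoints are PPP ASI50, PPP ASI75, PPP PGA 0/1 and PPP PGA pustules 0/1, all at Week 16.

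- **Logistic model.** SAP 7.5.2: "Fixed classification effects will include treatment and region (Japan vs. Non-Japan"). Protocol 7.2.3 agrees: "a logistic regression model on each binary endpoint at Week 16 with fixed factors for 'treatment', and 'region' as strata". Neither text names a baseline term or explains its absence.
- **Use of the estimates.** The dose-group response estimates from this model, or from its Firth version, "will be used as basis for the MCPMod analysis of the binary secondary endpoints", on the logit scale. Firth is used only when some dose-by-region cell has no events.
- **Other Week 16 models.** The primary MMRM in SAP 7.4 is coded "MODEL ept = stratum visit*trt base*visit / ddfm=kr s CL", so baseline enters at every visit. SAP 7.5.2 analyses continuous secondary endpoints up to Week 16 in the same way.
- **Availability.** SAP 6.3 limits the FAS to randomised patients who "received at least one dose of study drug and had a baseline for the primary endpoint", so every FAS patient has a baseline PPP ASI.

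The R code that the SAP cites (Sections 9.2 and 9.4) is not in the public text, so only the written model can be checked.

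**The concern.** Among the Week 16 efficacy models, only the binary ones leave baseline out. PPP ASI50 and ASI75 are cut-points on the same percent change that the primary model adjusts for baseline. The two PGA endpoints are absolute end states, which could depend on where the patient started.

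The arms are small: "40, 20, 20, 20 and 40 for placebo and low to high dose regimes respectively". Randomisation is stratified by region only. Between a 20-patient arm and a 40-patient arm, the standardised baseline difference has SD √(1/20 + 1/40) = 0.27, so a gap above 0.3 SD arises by chance in about 27% of such comparisons.

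If baseline predicts response, the unadjusted risk differences vary more than they need to and the binary dose-response test loses some power. Only the secondary endpoints are at stake.

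**Working it through.** **1. Reproduce the plan's own figure.** The plan gives no power or precision figure for a binary endpoint. The nearest is Protocol Table 7.5: 1 for the primary endpoint.

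- Inputs: SD 35, values floored at −100, arm means −25, −40, −44, −51, −55 and arm sizes 40/20/20/20/40, with the contrasts of SAP Table 7.4: 2.
- Model weights were taken as exp(−0.5·AIC), the usual form. SAP 7.4 prints no minus sign.
- Result over 4,000 runs, linear curve: 76.1% against the stated 77.1% (delta 25), and 92.3% against 93.2% (delta 20). This is close enough to rely on the set-up.

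**2. Implied response rates.** With the same normal assumptions and no floor, P(response) = Φ((cut-point − mean)/35).

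- ASI50: placebo Φ((−50+25)/35) = 23.8%; high dose Φ((−50+55)/35) = 55.7%. All arms, placebo to high: 24/39/43/51/56%.
- ASI75: placebo Φ((−75+25)/35) = 7.7%; high dose Φ((−75+55)/35) = 28.4%. All arms: 8/16/19/25/28%.
- The placebo ASI50 rate matches the 5 of 21 (23.8%) that Protocol 1.2 reports for the earlier PPP trial.

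**3. Models with and without baseline.** The correlation rho between baseline and percent change is an assumption, because the documents give none. Each setting used 3,000 runs, regions split 50:50, and Firth logistic fits throughout. MCPMod is the one-sided 5% test. The variance fall is 1 − 1/(relative efficiency), where relative efficiency is the variance without baseline divided by the variance with it.

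| rho | ASI50 rel. efficiency (variance fall) | ASI50 MCPMod power, without → with | ASI75 rel. efficiency (variance fall) | ASI75 MCPMod power, without → with |
|---|---|---|---|---|
| 0 | 1.001 (0.1%) | 91.4 → 91.2% | 0.995 (−0.5%) | 75.9 → 76.0% |
| 0.2 | 1.021 (2.1%) | 91.7 → 92.3% | 1.005 (0.5%) | 76.8 → 77.3% |
| 0.3 | 1.049 (4.7%) | 91.6 → 92.7% | 1.025 (2.4%) | 76.9 → 79.0% |
| 0.4 | 1.095 (8.7%) | 91.1 → 93.8% | 1.054 (5.1%) | 76.3 → 79.7% |
| 0.5 | 1.154 (13.3%) | 91.7 → 95.4% | 1.104 (9.4%) | 76.3 → 81.1% |

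A separate large-sample calculation for 25% versus 50% responders gives variance ratios of 0.976 (rho 0.2) to 0.849 (rho 0.5), that is, falls of 2.4% to 15.1%. This sets the upper end of the range at rho 0.5.

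In patients, for the 80 in the high-versus-placebo comparison, the ASI50 gain is 80 × 0.049 ≈ 4 at rho 0.3 and 80 × 0.154 ≈ 12 at rho 0.5.

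**4. Scale of the gain.** On the logit scale, adjustment does not shrink the standard error. For ASI50 at rho 0.5 the SE of the high-versus-placebo log odds ratio rises from 0.501 to 0.556, while the estimate moves from 1.40 to a conditional 1.66. The ratio of estimate to SE goes from 1.40/0.501 = 2.79 to 1.66/0.556 = 2.99, which is where the power comes from.

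**5. Keeping the target.** The MCPMod powers in step 3 used those conditional logits. When the fitted probabilities are instead averaged over the observed baseline and region and then put on the logit scale, the target stays the arm response rate. The high-versus-placebo variance ratio is then about 0.98 at rho 0.2, 0.95–0.97 at 0.3 and 0.86–0.92 at 0.5, with essentially no loss at rho 0. At 0.86 the test statistic grows by 1/√0.86 = 1.08, in line with 2.99/2.79 = 1.07 in step 4. MCPMod power was not simulated separately for this version.

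**6. Validity.** With no treatment effect and rho 0.3 (ASI50), type I error was 4.0% without baseline and 4.1% with it.

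**The case against.** The strongest reply is that nothing is invalid. The protocol and SAP agree, the only stratification factor is in the model, and chance imbalance is already reflected in the standard error of a randomised comparison. No secondary endpoint is labelled key, and proof of concept rests on the baseline-adjusted primary analysis. All of this stands.

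Three stronger readings are tempting, and the documents do not support them.

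- **That precision is certainly being lost.** The loss depends on a correlation that is nowhere reported, and up to about 0.2 it is close to nil. Protocol 1.2 and 1.3 describe larger effects in patients with more severe disease. That is post hoc and concerns the treatment effect by severity; it does not show that baseline predicts response within an arm.
- **That adjustment tightens the arm logits used in MCPMod.** Conditional logits have a larger SE and a different target. The risk-difference gain carries over only if the logits are standardised.
- **That baseline matters equally for every binary endpoint.** ASI50 and ASI75 are already relative to the patient's own baseline. The primary endpoint is too, and the plan still adjusts it, so this weakens the case without removing it. For total PGA, entry requires a score of at least 3 on a 0–4 scale, so baseline PGA can only be 3 or 4. Neither PGA endpoint was simulated.

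It is also fair that the planned Firth switch does not by itself deal with few responders, since only an empty cell triggers it. The simulation used Firth throughout and so did not test that switch.

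**Conclusion.** The point holds as an optional improvement. The written binary models leave out a covariate that every FAS patient has and that the other Week 16 efficacy models use. The possible cost is on secondary endpoints only: about nothing at a baseline–response correlation up to 0.2, roughly 1–2 points of MCPMod power at 0.3, and 4–5 points at 0.5, with the variance reductions tabulated above. Little is risked if baseline proves uninformative.

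These sizes rest on the assumed correlation range, on response rates implied by the protocol's normal model with linear means, and on Firth fitting throughout. The hidden code may already carry a baseline term; the text does not say so.

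**What to change.** Before unblinding for the Week 16 analysis, amend SAP 7.5.2 as follows, or state why baseline is left out.

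1. Add mean-centred baseline PPP ASI as a continuous covariate to each binary model, beside treatment and region.
2. Define the reported risk difference as standardised: average each patient's fitted probability under each arm over the FAS, then take differences. The SAP now speaks only of predicted probabilities and does not say how covariates are averaged. With region in the model, that needs stating in any case.
3. Pass the standardised arm response rates on the logit scale, with their delta-method covariance, to the binary MCPMod.
4. Use the Firth fit for all binary models, or widen its trigger beyond an empty dose-by-region cell.

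The cost is one extra parameter where responders are few (about 8% on placebo for ASI75 under the plan's assumptions) and a standardisation step in the code. The Reeve interval is cited in the plan for logistic regression with covariates, so the same method can be kept. No new data are needed and no FAS patient is lost.

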7.7 EXTENT OF EXPOSURE

The number of subjects who received a dose of trial drug will be tabulated. The amount of treatment received as well as the amount injected [% of planned] will be summarised by descriptive statistics (N, mean, SD, minimum, median, maximum) for the loading stage, the maintenance stage up to week 16, overall up to week 16 (primary analysis only), and the maintenance stage post week 16 (final analysis only), as well as the overall dose across all stages (final analysis only).

7.8 SAFETY ANALYSIS

All safety analyses will be performed following BI standards. No hypothesis testing is planned. OC-IR and OR methods will be used for safety reporting.

In primary analysis, AE and possibly clinically significant laboratory abnormalities up to week 16 will be analyzed. In final analysis, AE and possibly clinically significant laboratory abnormalities up to and post the first maintenance treatment at or after week 16 will be analyzed separately.

Primary analysis: AE and possibly clinically significant laboratory abnormalities up to week 16

The analysis will include all on-treatment events up to the treatment at week 16 based on SAF. If patient early discontinued from treatment prior to week 16 or missed week 16 treatment, then the on-treatment events up to Day 127 (the right limit of the extended week 16 visit window) will be included.

Final analysis: AE and possibly clinically significant laboratory abnormalities prior to the first maintenance at or after week 16

The analysis will include on-treatment events up to the first maintenance treatment at or after week 16 based on SAF. If a patient early discontinued from treatment prior to week 16, then the patient's events up to the end of REP of the last treatment will be included.

One additional group will be reported for AE and possibly clinically significant laboratory abnormalities, which is the combination of Arm 1, 2, 3 and 4 ("Speso Total").

Final analysis: AE and possibly clinically significant laboratory abnormalities post the first maintenance at or after week 16

The analysis will include on-treatment events post the first maintenance treatment at or after week 16 based on SAF-post 16. Only patients who have received at least one dose of treatment at or after week 16 will be included.

For AE and possibly clinically significant laboratory abnormalities, except for 5 treatment arms of the trial, one additional group will be reported which is the combination of Arm 1, 3 and 5 [REDACTED]

As the onset time of an AE will not be collected in the trial, any AE which occurs on the same day as a treatment dose will be assigned to the "post treatment". For safety assessments by visits, if time is not collected, data on the same day of a treatment dose will be treated to be "prior treatment" except for scheduled local tolerability and post-dose vital signs assessments.

Off-treatment data will be listed only

Additional analyses on AE will be also included:

AE within loading stage

For AE, the additional safety tables for loading dose stage will be produced by re-grouping patients based on their loading doses [REDACTED] using SAF. The outputs

will include on-treatment data up to the first maintenance dose at week 8. If patient early discontinued from treatment prior to week 8 or missed treatment at week 8, then the safety data up to Day 71 (the right limit of the extended time window of week 8) will be included:

- Overview on TEAE
- TEAE by SOC, preferred term
- Serious TEAE
- All AESI
- UDAEC

AE over on-treatment period

In the final analysis, the additional selected tables for the overall period will be produced based on SAF to report AE occurring during whole treatment period from Day 1. Note that only Arm 1-4 will be reported:

- Overview on TEAE
- TEAE by SOC, preferred term
- Serious TEAE
- All AESI
- UDAEC

